Nocturnal, sleep-related slowing of LH pulse frequency during the early follicular phase is well described. Our data (above) and several studies by Loucks and colleagues (53-55) suggest that late follicular LH pulse frequency also slows by 20-30% during sleep. Nocturnal slowing of LH frequency in the early follicular phase (and presumably in the late follicular phase) appears to be specifically related to sleep and is likely driven by higher CNS systems.

These nocturnal changes in LH pulse frequency are interesting in light of what is observed during puberty. In early pubertal girls (and boys), nocturnal LH frequency *increases* compared to daytime LH frequency. It is generally believed that the overnight increase of LH pulsatility during puberty is driven by higher CNS systems.

Of particular interest, our preliminary data in peripubertal girls suggests that nocturnal LH frequencies in early pubertal girls, late pubertal girls, and the 8 adult women studied under JCM016 are very similar, while late evening LH frequencies (i.e., from 1900-2300 h – a surrogate for daytime frequency) are varied (Figure 2). These data are consistent with the notion that higher CNS systems may in large part determine nocturnal GnRH pulse frequency during puberty and in adults. Accordingly, sleep-associated (and presumably CNS-driven) LH frequency may be similar in pubertal girls and adult women, with daytime frequencies being controlled by other factors.

In addition, two of the aforementioned studies by Loucks and colleagues reported that dietary restriction slows daytime—but not nighttime—LH pulse frequency in the late follicular phase (53, 55). This suggests that daytime and nighttime LH frequency may be differentially affected by experimental maneuvers.

On the basis of the above observations, we have considered the possibility that *daytime* (or non-sleep-associated) LH frequency is acutely responsive to changes in P concentrations in women, even though nighttime frequency is not. This would be consistent with the notion that CNS control of *nocturnal* LH frequency may override hormonal control, at least in the short-term. We would like to test this hypothesis by using a protocol identical to the earlier JCM016 protocol except that the timing of the sampling and P (and PBO) administration is altered by exactly 12 hours (e.g., P and PBO are administered at 0600 h instead of 1800 h).

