**4. What is your plan for primary variable analysis?**

Data analysis plan: 10-h LH pulse frequency will be analyzed using hierarchical mixed-effects ANOVA models. Each ANOVA model will be structured to examine whether exogenous P affects LH frequency. In the ANOVA model, “subject” will be a blocking factor, while the treatment condition (placebo, P) will be modeled as highest within-subject level factor, and the measurement assessment time (10-h baseline sampling period, 10-h post-treatment sampling period) will be modeled as the lowest within-subject level factor. Treatment by measurement assessment time interaction will also be modeled. We will use linear-contrasts of the ANOVA least-squared means to test our a priori research hypothesis. Specifically, we will test whether the change in mean LH frequency from the baseline state to the post-

treatment state differed depending on whether placebo or P was administered at 0600 h. 95% confidence interval construction (for the estimation of the true magnitude of P effect) will be based on the t-distribution. Traditional residual diagnostics will be conducted to evaluate model goodness of fit. If LH frequency data fail to adhere to equal variance and normality assumptions of linear mixed-effects models, the data will be analyzed using a generalized linear mixed-effect-model in a similar format, with the exception that LH pulses as will be modeled as counts utilizing either a Poisson or a Negative-Binomial distribution. Similar statistical procedures will be used to compare the effects of P in controls vs. PCOS: in the ANOVA model, PCOS status (no, yes) will be a between-subject factor, while the treatment (placebo, progesterone) will be a within-subject factor.

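### Read literally, the nested ANOVA keeps woman-to-woman differences in the night-to-day shift in the error of the primary contrast; if women differ appreciably in that shift, the interval is too wide and power is lost

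*Combined protocol and SAP*

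**What the plan says.** Statistical Considerations item 4 sets out a hierarchical mixed-effects ANOVA. Subject "will be a blocking factor". Next, "the treatment condition (placebo, P) will be modeled as highest within-subject level factor". Below that, assessment time, with one 10-h window before dosing and one after, "will be modeled as the lowest within-subject level factor". The plan adds: "Treatment by measurement assessment time interaction will also be modeled". The primary test is a linear contrast asking whether the change from baseline to post-treatment differs between P and placebo, and "95% confidence interval construction (for the estimation of the true magnitude of P effect) will be based on the t-distribution". The item names no random terms, covariance structure or rule for degrees of freedom.

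Two other places state the purpose of the design. Study Design item 1 makes each woman her own control. Biomedical Research item 1 says that the change after P is to be standardized to the change after placebo.

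Sampling starts at 2000 h and dosing is at 0600 h, so the 10-h baseline is 2000-0600 h, with sleep encouraged from 2200 h. The 10-h post-treatment window is 1000-2000 h, when sleep is not allowed. The Background reports that "late follicular LH pulse frequency also slows by 20-30% during sleep".

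**The concern.** The design gives each woman a baseline and a post-treatment window at both admissions. Whatever her own night-to-day shift is, it enters both of her changes and drops out when one is subtracted from the other. The natural error for the primary contrast is therefore the spread of that within-woman difference.

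A model that nests time under admission and admission under woman pairs the data on a woman's overall level but not on her change. Its lowest-level error pools two sources: woman-by-time, and woman-by-treatment-by-time. The first does not affect the estimate but inflates its standard error.

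At stake is sensitivity. With 12 women per group, a real slowing could be missed and read as evidence that P does not acutely slow daytime LH pulses.

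**Working it through.** **Inputs from the plan.** Item 3: 12 women per group completing both admissions; SD 20.6 min and 1.24 pulses/10 h; minimum detectable effects 16.7 min and 1.0 pulse/10 h at 80% power or more. Two-sided 5% is taken from the 95% interval in item 4.

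**Assumed.** The correlation r between a woman's two changes is not given; 0 to 0.5 is shown. The SD of 1.24 is taken as the SD of the paired difference D = (post - baseline on P) - (post - baseline on placebo). Item 3 does not define it that closely.

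**1. The plan's own figure.** (1.960 + 0.842) × SD/√12 gives 16.66 min for SD 20.6 (stated 16.7) and 1.003 pulses for SD 1.24 (stated 1.0). Both reproduce by the normal approximation. The same number arises from SD × √(2/24), that is, a single-change SD with 24 women, so the figure does not settle which SD is meant.

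**2. The two error terms.** Let σ²wt be the woman-by-time variance and σ²e the residual variance. Each change has variance 2(σ²wt + σ²e), and r = σ²wt/(σ²wt + σ²e).

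- Paired: SE = SD(D)/√n on n-1 = 11 df. Here 1.24/√12 = 0.358, whatever r is.
- Nested, with complete data and admission variance estimated above zero: the test equals an unpaired t test on the changes, SE = SD(D)/√(n(1-r)) on 2(n-1) = 22 df.

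**3. Break-even.** The ratio of nested to paired interval width is about (2.074/2.201)/√(1-r). It equals 1 when r = 1 - (2.074/2.201)² ≈ 0.11. Below that, the extra degrees of freedom make the nested interval slightly narrower.

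**4. Power and type I error** (simulated; n = 12, SD(D) = 1.24, effect 1.0):

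| r | Nested SE | Nested power | Paired power | Nested type I error | Width ratio (formula) |
|---|---|---|---|---|---|
| 0 | 0.358 | 76% | 72% | 5.0% | 0.94 |
| 0.11 | 0.380 | 72% | 72% | 3.9% | 1.00 |
| 0.2 | 0.400 | 68% | 72% | 3.0% | 1.05 |
| 0.33 | 0.438 | 60% | 72% | 1.9% | 1.15 |
| 0.5 | 0.506 | 46-47% | 72% | 0.9% | 1.33 |

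Paired type I error stays at 5%. The pulse-interval endpoint behaves the same way: at 16.7 min, nested power is 76%, 68% and 47% at r = 0, 0.2 and 0.5, and the paired mean half-width is about 12.8 min throughout.

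**5. One illustrative REML fit** to simulated data with woman-by-time variation. The contrast SE is 0.661 with random woman and admission, and 0.409 once woman-by-time is added, equal to the paired SE of 0.409. The unpaired-change SE is 0.713. The nested fit falls short of 0.713 because its admission variance was estimated near zero, so the equality in step 2 is for the ordinary ANOVA strata.

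**6. Does the added term always work?** Its ANOVA estimate is negative when an F(11, 11) variable falls below 1/(1 + 2k), with k = σ²wt/σ²e = r/(1-r). The probability is 50% at r = 0, 36% at r = 0.11 and 13% at r = 0.33. REML then typically sets the variance to zero and returns the nested error.

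**The case against.** **The random structure is inferred.** Item 4 speaks of highest and lowest within-subject levels but lists no random terms. A crossed repeated-measures model also treats both factors as within-subject, and the plan elsewhere says that each woman is her own control. This stands: the split-plot is the natural literal reading, not a documented specification.

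**Variation between women is not documented.** The 20-30% slowing in sleep is an average, and a shift common to all women is absorbed by the fixed time effect. Only differences between women in that shift matter, and no section reports them. This also stands. A night window set against a waking window, with sleep encouraged rather than controlled, makes some variation plausible but gives no size.

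**A reader might infer that the interval is certainly too wide and power certainly lost.** The documents do not support that. Below r of about 0.11 the nested model does slightly better (76% against 72% at r = 0).

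**A reader might carry the figures over to the other analyses.** For PCOS against controls, item 4 names only PCOS status and treatment, with no time level, which is compatible with analysing per-woman changes. The secondary outcomes in item 5 include 30-min and 2-h series, to which this two-by-two calculation does not transfer directly.

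**The error is at worst conservative.** That is correct: a positive result would stand.

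**Conclusion.** The point holds conditionally. On the literal reading of item 4, the primary contrast is judged against an error that includes woman-by-time variation, contrary to the pairing the crossover was designed for. If r exceeds about 0.11 with 12 women, the interval over-covers and power falls: by about 4 points at r = 0.2, 12 at r = 0.33 and 25 at r = 0.5. These sizes rest on an assumed r and on taking 1.24 as the SD of the paired difference.

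The trade-off is uneven. The paired analysis holds 5% type I error and about 72% power whatever r is, and gives up at most about 4 points when r = 0. That 72% is itself below the intended 80% because the stated detectable effect uses the normal approximation; this is a separate matter that changing the error term does not cure.

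**What to change.** - Make the primary analysis the per-woman contrast: (post minus baseline on P) minus (post minus baseline on placebo), with a t-based 95% interval on n-1 degrees of freedom.
- For hypothesis 2, compare that per-woman value between PCOS and controls.
- If a mixed model is kept, list its random terms and degrees-of-freedom rule, include woman-by-time alongside woman and admission, and do not let the error fall back to the nested term when that variance is estimated at zero.
- In item 3, say whether the SD is that of a single change or of the paired difference.
- State the error structure for the 30-min and 2-h secondary series separately.

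No new data are needed. Error degrees of freedom fall from 22 to 11 per group, which costs about 4 points of power (76% to 72%) if women do not differ at all in their night-to-day shift.

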## Background

### 1. Provide the scientific background, rationale and relevance of this project.

It remains unknown how rapidly progesterone (P) affects gonadotropin releasing hormone (GnRH) pulse frequency slowing in normal women or in women with PCOS. Through this study, we are pursuing this question to confirm an important assumption in our overall hypothesis regarding how cyclic ovulation is established during puberty.

GnRH stimulates LH and FSH synthesis and secretion from the same gonadotrope cell; nonetheless, LH and FSH levels change differentially throughout ovulatory cycles, with FSH predominance in the early follicular phase and LH predominance in the late follicular phase (1-7). These variations in gonadotropin secretion result in part from different patterns of pulsatile GnRH stimulation, with fast GnRH pulse frequencies favoring LH and slow GnRH pulse frequencies favoring FSH synthesis and secretion (8-12).

In ovulatory women, LH (and by inference GnRH) pulse frequency slows from one pulse every 60-90 min in the follicular phase to approximately one pulse every 4-6 h during the luteal phase. Luteal slowing of GnRH pulse frequency increases FSH synthesis, but high luteal levels of estradiol (E2) and inhibin prevent FSH release from the gonadotrope (13, 14); when E2 and inhibin concentrations fall during the luteal-follicular transition (i.e., when inhibition of FSH secretion is removed), an increasing GnRH pulse frequency leads to the early follicular monotropic rise of FSH. Thus, the ability to slow GnRH pulse frequency during the luteal phase appears to be important for the early follicular rise in plasma FSH and, therefore, follicular development.

Progesterone appears to be the primary effector of GnRH pulse frequency slowing. GnRH pulse frequency slows coincident with P increases in the luteal phase, and administration of P to women during the follicular phase also slows GnRH pulse frequency (15), although the rapidity with which this occurs is unknown. Progesterone's ability to slow GnRH pulse frequency appears to require the permissive presence of E2 (16, 17), possibly reflecting E2's ability to induce hypothalamic P receptors (18-21).

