**3. Provide a justification for the sample size used in this protocol.**

Sample size/statistical power: The primary endpoint will be the change in LH pulse frequency (over 10 h) attributable to P. The null hypothesis is that 10-h (1000-2000 h) LH frequency after P administration will be the same as 10-h (1000-2000 h) LH frequency after placebo administration. Estimates of within-subject variability utilized in the calculation (column 2 of table below) were based on our preliminary data. Assuming that 12 women in both groups complete both CRU admissions (placebo admit, P admit), we list in column 3 (table) the estimates for the minimum detectable absolute difference between the mean change in 10-h LH pulse frequency that would provide ≥ 80% statistical power.

Endpoint	Within-subject standard deviation	Minimum detectable P effect on LH frequency
Change in LH pulse-interval (min)	20.6	16.7
Change in # of LH pulses / 10-h	1.24	1.0

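### If the linear-model checks fail, the Poisson or negative-binomial fallback would overstate standard errors about 3 to 5 times on the readings that reproduce the sample-size table; the error is conservative

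*Combined protocol and SAP*

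**What the plan says.** Statistical Considerations, item 4, analyses 10-h LH pulse frequency with a hierarchical linear mixed model. The test is whether the change from the baseline window to the post-treatment window differs between the progesterone and placebo admissions. Confidence intervals use the t-distribution.

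The fallback has a stated trigger: "If LH frequency data fail to adhere to equal variance and normality assumptions of linear mixed-effects models". The data then go to a generalized linear mixed model in a similar format, "with the exception that LH pulses as will be modeled as counts utilizing either a Poisson or a Negative-Binomial distribution". The text does not mention a scale parameter, quasi-likelihood or robust standard errors. The second primary hypothesis inherits the same route: "Similar statistical procedures will be used to compare the effects of P in controls vs. PCOS".

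Item 3 (sample size) gives a within-subject SD of 1.24 for "Change in # of LH pulses / 10-h" with a minimum detectable effect of 1.0, and an SD of 20.6 min for the pulse interval with a minimum detectable effect of 16.7 min.

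The Background gives the expected rate: "LH (and by inference GnRH) pulse frequency slows from one pulse every 60-90 min in the follicular phase". It also reports that "late follicular LH pulse frequency also slows by 20-30% during sleep". The baseline window runs from 2000 to 0600 h and so includes the night.

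**The concern.** Given the woman, a Poisson model sets the variance of a window's count equal to its mean. A negative-binomial model sets it at mean + k × mean², with k not below zero, so at or above the mean. LH pulses are much more regular than that. A Poisson count with mean 6.7 to 10 has an SD of 2.6 to 3.2, while the protocol reports 1.24.

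A model that cannot represent this regularity attaches too much noise to the treatment contrast. Offering negative binomial as the alternative does not help, because with under-dispersed counts its best fit is k = 0, which is Poisson again.

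If the switch is made, a real effect of the size the study was planned around could be reported as no effect, with an interval too wide to be informative. The Background already reports no acute effect of progesterone on night-time frequency, so a spurious null by day could easily be taken as agreeing with it.

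**Working it through.** **Inputs.** SD 1.24 pulses and 20.6 min, 12 women per group (item 3). Pulse rate from the Background: 600/90 = 6.67 to 600/60 = 10 pulses per 10 h. Two-sided 5% is assumed, because item 3 states no alpha.

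**Step 1: reproduce the sample-size table.** (1.960 + 0.842) × 1.24/√12 = 1.003 and 2.802 × 20.6/√12 = 16.66, against the stated 1.0 and 16.7. The same values follow from 1.24 × √2 with 24 women. If 1.24 is the SD of a single 10-h count, the contrast SD is 2 × 1.24 = 2.48. The detectable effect is then 2.01 with 12 women or 1.42 with 24, and neither matches.

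**Step 2: mean implied by the two SDs.** The interval is about 600/N, so SD(interval) ≈ 600 × SD(N)/N². Setting 20.6 = 600 × 1.24/N² gives N = 6.01, close to the lower end of the Background range.

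**Step 3: variance against mean.** The contrast D for each woman combines four window counts, so Var(D) = 4 × window variance.

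| Reading of 1.24 | SD of D | Window variance | Variance/mean at 6.67, 10 | Variance/mean at 6.01 |
|---|---|---|---|---|
| (a) SD of the difference in changes (fits with 12) | 1.24 | 0.384 | 0.058, 0.038 | 0.064 |
| (b) SD of one admission's change (fits with 24) | 1.754 | 0.769 | 0.115, 0.077 | 0.128 |
| (c) SD of one 10-h count (does not fit) | 2.48 | 1.538 | 0.231, 0.154 | 0.256 |

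Poisson requires 1.

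**Step 4: factor on the standard error.** With equal window means μ and scale 1, Poisson gives D an SD of 2√μ. The factor is 2√μ/SD(D).

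- (a) 5.164/1.24 = 4.16 to 6.325/1.24 = 5.10
- (b) 5.164/1.754 = 2.94 to 6.325/1.754 = 3.61
- (c) 5.164/2.48 = 2.08 to 6.325/2.48 = 2.55

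At 6.01 pulses the factors are 3.95, 2.80 and 1.98. If both baseline windows are 30% slower, the log-scale factor is √Σ(1/m) ÷ [s × √Σ(1/m²)], with m the window means and s the window SD. This is 0.89 of the equal-means value, about 10% smaller.

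**Step 5: power for the stated 1.0-pulse effect, 12 women.** The true SE is SD(D)/√12. Paired t-test power uses the noncentral t with 11 df. Fallback power is approximately Φ(1/SE − 1.96 × factor), shown at 6.67 pulses, the more favourable end.

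| Reading | True SE | Paired t-test | Fallback |
|---|---|---|---|
| (a) | 0.358 | 72% | Φ(2.79 − 8.16), about 0% |
| (b) | 0.506 | 44% | Φ(1.98 − 5.77), below 0.1% |
| (c) | 0.716 | 25% | Φ(1.40 − 4.08), about 0.4% |

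Simulation on whole-number counts, with the baseline 0% or 30% slower, agrees: fallback power is 0–1% and type I error is at most about 0.1%. With 24 women under (b), the paired t-test has 76% power. The fallback has Φ(2.79 − 5.77), about 0.1%.

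Larger effects fare better. With 12 women, the fallback detected a 3-pulse effect in about 15–95% of simulated trials and a 4-pulse effect in about 80–100%, depending on reading and mean.

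**Step 6: controls versus PCOS.** If both groups share the same mean and variance, each group's contrast has its SE inflated by the same factor, and so does their difference. No PCOS pulse rate or SD is given, so this is an assumption.

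**The case against.** The strongest reply is that the figures describe the wrong data. The plan switches only when the checks fail, yet the arithmetic and simulation use roughly normal, equal-variance counts. Item 4 names no test. If Shapiro-Wilk and Levene tests at 5% are assumed, one or the other fails in roughly 6–13% of trials simulated in this way. Data that truly fail, through outliers or a variance that changes with frequency, could have a different variance-to-mean ratio. This stands: the sizes are illustrative. The mismatch is wide, though. Even under reading (c), the variance would have to be about four times larger to reach a mean of 6.67 (6.67/1.538 = 4.3).

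Second, item 4 is silent on scale, and an alert analyst could estimate it or add robust standard errors. The fallback follows a sentence on t-based intervals and is to run in a similar format. This stands in part. Scale 1 is not stated, but it is what a plain Poisson model means, and nothing in the text asks for anything else.

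Third, the consequences are limited. The linear model is primary, the pulse-interval measure in item 3 is not a count and is unaffected, and large effects would mostly still be found. All of this stands.

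**Conclusion.** The named fallback does not suit the counts that the protocol describes, and the direction is the same under all three readings of 1.24. At 6.7 to 10 pulses the standard error would be overstated by a factor of 4.2–5.1 or 2.9–3.6 on the two readings that reproduce the sample-size table. The 2.1–2.6 range rests on a reading that does not reproduce it. The sizes assume scale 1, equal window means and approximately normal counts.

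A reader might infer that the primary analysis is itself unsound, or that the trial loses most of its power. The documents do not support that. The fault applies only after a switch whose frequency cannot be determined from them, so no overall loss of power can be stated. Nor does the fallback raise the risk of a false positive, since its type I error is near zero. The risk is a missed effect or an over-wide interval. This is a minor point, worth settling because it touches both primary hypotheses and is cheap to correct.

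**What to change.** In Statistical Considerations, item 4, replace the fallback clause with one that allows variance below the mean. Suggested wording: *If the checks fail, pulse counts will be analysed with a log-linear model with estimated dispersion (quasi-Poisson) and a t reference distribution; the same fallback will be used for the comparison of controls with PCOS.* In simulation this held type I error at 4–5%.

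An equally acceptable clause keeps the linear mixed model, with window-specific residual variances and small-sample robust standard errors. A sign-flip test on the within-woman differences in change could be added as support.

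The cost is one clause and a little programming, with no extra participants, samples or visits. Writing it down in advance also avoids choosing the variance model after seeing the data.
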